1.0 OBJECTIVES AND ENDPOINTS

Objectives	Endpoints/ Measurements
Primary Objective	

 To observe the effect of the Sip2Sleep® product on sleep quality for participants with self-reported sleep disturbance 	
 Change in average sleep quality score by 1 point as measured by daily 10-point visual analogue rating scale (VAS) from baseline and 1 week of no product use
Secondary Objectives	

 To assess the effect of Sip2Sleep® product on symptoms of sleep disturbance To assess the effect of Sip2Sleep® product on anxiety To assess the effect of Sip2Sleep® product on the level of alertness during the daytime 	
 Change in Insomnia Sleep Index (ISI) by 4.5 points from baseline and 1 week of no product use Change in Generalized Anxiety Disorder-7 (GAD-7) by 4.5 points from baseline and 1 week of no product use Change in average level of alertness during the daytime score by 1 point as measured by daily 10-point visual analogue rating scale (VAS) from baseline and 1 week of no product use
Exploratory Objectives	

 To observe the change in sleep duration via personal health tracking wearable device To observe the change in sleep latency via personal health 	
 Change in average nightly sleep duration as measured via personal health tracking wearable device from baseline and 1 week of no product use Change in average nightly sleep

tracking wearable device
 
3. To identify improvements for future participant-centered study designs using feedback
	
latency as measured via personal health tracking wearable device from baseline and 1 week of no product use
 
3. Assessment of patient satisfaction survey of study experience including design and use of app-based data collection tools

---	--

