4.0 STUDY ACTIVITY CALENDAR

Table 4.1 Study Calendar

Protocol Activities	Screening ^a	Study Duration ^b				
		Baseline	Product Use ^c	No Product Use	Product Use ^c	End of Study
Week	Up to 1 Week	Week 1	Week 2	Week 3	Week 4	
Day	Day -7 to -1	Day 1	Day 8	Day 15	Day 22	Day 29
Informed Consent	X					
Demographics	X					
Medical History	X					
Insomnia Severity Index	X	X	X	X	X	X
Eligibility	X					

Daily Objective Data Collection and Surveys ^d		X	X	X	X	X
Use of Study Product			X		X	
Generalized Anxiety Disorder-7		X	X	X	X	X
Experience Survey						X

- a. Screening to occur within 7 days prior to Baseline (Day 1)
- b. Planned duration of study is 4 weeks
- c. Participants to consume Sip2Sleep[®] product 30-60 minutes prior to lying down in bed.
- d. Participants will complete daily surveys to review objective data from wearable device collection and answer questions about their prior night’s sleep quality and level of alertness since waking.

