- Administer nightly dose of study product 30-60 minutes prior to lying down in bed through Day 28.

End of Study (Day 29):

- Complete Insomnia Severity Index and Generalized Anxiety Disorder-7.
- Complete surveys to review objective data (sleep duration and sleep latency) from wearable device collection and answer questions about their prior night's sleep quality and level of alertness since waking.
- Complete Experience Survey.

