9.1 Sample Size Estimation and Justification

We anticipate needing to screen approximately 200 individuals to enroll up to 80 individuals and achieve a final sample size of approximately 47 evaluable participants. For our primary outcome (i.e. change in average sleep quality VAS scores), we assume a common standard deviation = 2 and a conservative 0.50 correlation between VAS scores. We will have at least 90% power to detect a mean VAS score difference of 1 with $\alpha = 0.05$ using a two-sided Wilcoxon signed-rank test for the difference between dependent means with a final sample of 47 participants. Previous research on participants with insomnia and depression have suggested that single item sleep quality score can effectively detect meaningful changes in sleep quality over time relative to lengthier questionnaires.¹⁶

The secondary objectives include evaluating changes in the ISI, GAD-7 and daytime alertness VAS score. As above, we anticipate at least 90% power to detect a 4.5-point change in the ISI and GAD-7 with an expected standard deviation of 5. For daytime alertness, we anticipate at least 90% power to detect a 1-point change with an expected standard deviation of 2.

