12.5 Alternatives to Participation, Withdrawal, and Early Termination

Alternatives to Participation

The individual can choose not to participate.

Participant Withdrawal from Research/ Research Activities

Research activities are limited to five weeks.

Participants may withdraw from the study at any time and for any reason without prejudice. The withdrawal must be documented.

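### The Experience Survey, the only measure of exploratory objective 3, is scheduled only on Day 29, so its feedback describes only participants still responding then

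*Combined protocol and SAP*

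**What the plan says.** Section 1.0 states exploratory objective 3 as "To identify improvements for future participant-centered study designs using feedback". The matching endpoint is "Assessment of patient satisfaction survey of study experience including design and use of app-based data collection tools".

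Table 4.1 (Section 4.0) has one row for this, "Experience Survey", with a single mark in the End of Study column, Day 29. Section 6.1 lists it once, again on Day 29: "Complete Experience Survey". The objectives table speaks of a satisfaction survey and the schedule of an experience survey. No other such instrument appears, so I take them to be the same.

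On leaving the study, Section 12.5 says: "Participants may withdraw from the study at any time and for any reason without prejudice. The withdrawal must be documented". No exit survey, early-termination assessment or contact with leavers is described. Section 9.1 plans to "enroll up to 80 individuals and achieve a final sample size of approximately 47 evaluable participants". Sections 12.2 and 12.4 tie the $25 payment to completion.

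**The concern.** The objective is to find faults in the design and the app tools so that later studies can do better. Daily surveys, wearable data review and app use over four weeks are plausible reasons to stop, and they are also what the survey asks about. The selection may therefore act on the quantity being measured: those who found the design tolerable stay to be asked, and those who did not are gone. Analysis cannot repair this afterwards, because no feedback is collected from leavers, and the missing-data rules in Section 9.5 cannot supply it. At stake is how far the satisfaction result and the list of suggested improvements can be taken to speak for everyone who enrolled.

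**Working it through.** **Schedule.** Objective 3 has one endpoint (Section 1.0). Its instrument has one time point, Day 29 (Table 4.1 and Section 6.1). The only planned action at withdrawal is documentation (Section 12.5). Followed exactly, the plan gathers no survey feedback from anyone who withdraws before Day 29. This is inferred from the absence of any exit procedure; no section states it outright.

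**The plan's own figures.** The 47 in Section 9.1 reproduces. With SD 2 and correlation 0.50, the SD of the paired difference is sqrt(2 × 2² × (1 − 0.50)) = 2. For a difference of 1, two-sided alpha 0.05 and n = 47, power for the Wilcoxon signed-rank test is 0.906 (paired t power with n multiplied by 3/π) and 0.908 by simulation (20,000 runs, normal differences). With n = 46 the first method gives 0.8995. Nothing here depends on the survey.

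**Possible loss.** 80 − 47 = 33, and 33/80 = 41.25%. This is the largest number the plan allows to be non-evaluable, at the enrolment ceiling. It is not a dropout rate: under Section 9.3 a participant can reach Day 29 and answer the survey, yet fail the 60% diary rule or lack wearable data.

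**Size of the overstatement.** Let f be the share of enrolled participants who leave before Day 29, S the proportion satisfied among those who stay and L the proportion among leavers. Assume everyone who stays answers.

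- The survey reports S.
- The value across all enrolled is (1 − f) × S + f × L.
- The difference is f × (S − L).

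The documents give neither f nor S − L, so both are assumptions:

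| Share leaving early (f) | Gap 20 points | Gap 40 points |
|---|---|---|
| 10% | 0.10 × 20 = 2 | 0.10 × 40 = 4 |
| 20% | 0.20 × 20 = 4 | 0.20 × 40 = 8 |
| 41.25% (ceiling) | 0.4125 × 20 = 8.25, about 8 | 0.4125 × 40 = 16.5 |

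Entries are percentage points of overstatement. With no gap, the overstatement is zero at any rate of leaving.

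**The case against.** An end-of-study experience survey is a defensible choice. Respondents on Day 29 have used the whole design and every tool, so they are well placed to suggest improvements. The schedule does not restrict the survey to evaluable participants, so people who had syncing trouble or missed diaries but stayed can still report it. The objective is the third of three exploratory ones, it is descriptive and no test is attached. The documents contain no dropout rate, reasons for leaving, survey items or satisfaction data, so neither the direction nor the size of any bias is established. Documentation of a withdrawal might include a reason; the plan does not say either way.

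All of this stands, and it limits the point. A reader might infer that objective 3 cannot be answered at all. The text does not support that: it promises improvements identified from feedback, not a satisfaction rate for all enrolled or an account of why people left, so the objective can be answered for those who reach Day 29. A reader might also take 41% as expected attrition, or treat upward bias as certain. The first is a ceiling on non-evaluability, and the second is plausible but unproven. What the objection does not remove is that the plan provides no way to hear from those who leave early.

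**Conclusion.** The point holds as a limited one. The only measure of exploratory objective 3 is taken once, on Day 29, so its result describes participants still responding then and is likely, though not shown, to under-represent problems with the design or the app. Under the assumed inputs the overstatement of satisfaction runs from 2 points (10% leaving, 20-point gap) to 16.5 points (41.25% leaving, 40-point gap). The upper end requires all 33 potentially non-evaluable participants to leave before Day 29, which the plan does not predict. No primary or secondary endpoint and no power statement is affected. This is an optional, low-priority improvement to an exploratory objective.

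**What to change.** In Table 4.1 and Section 6.1:

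- At documented withdrawal, offer the same survey in CHLOE, voluntarily, with one added item on the reason for stopping.
- On Day 29, send the survey to every enrolled participant who has not withdrawn, including those who stopped submitting daily surveys. Each person is then surveyed once.

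In the analysis section, report responses and response rates separately for completers and early leavers, and describe the Day-29 result as feedback from those who reached Day 29.

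Tying the exit survey to documented withdrawal is cleaner than triggering it after a run of missed diaries. Someone who misses 5 consecutive days of the 14 product-use days still has 9/14 = 64%, which meets the 60% rule if that rule is applied to the two product-use weeks together. Such a person could be asked why they stopped while still in the study, and then be surveyed again on Day 29.

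The cost is one app trigger for an existing survey, one item and a short IRB amendment. The downsides are that response among leavers will probably be low and the satisfaction figure may be less favourable. The sample size does not change.

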7.0 DATA COLLECTION AND MANAGEMENT

7.1 Data Collection Elements, Source, and Method of Collection

For recruitment purposes only, a data set limited to name, email, telephone number, and Study ID number will be generated manually. For analysis, data from the assessments and sleep data will include the Study ID number and demographic factors (age, gender, race, ethnicity), medications, and supplements.

7.2 Data Management

Research Data Capture System

This project will be utilizing People Science's proprietary platform, CHLOE. All data is securely stored on People Science Amazon Web Services HIPAA compliant servers. The platform contains modules for building and managing forms / surveys, landing pages, marketing outreach with tracking tools for recruitment, audited electronic consent forms, data management and analytics using an integrated relational database. Data from completed assessments will automatically be collected for analysis. Study monitoring can be done using reporting features.

7.3 Data Management at Study Completion

For longer term storage of the data that will reduce risk of a data breach while still permitting that the data be verifiable (audited) the dataset will be de-identified - no names, etc., and all dates turned into time- and coded, and the key to the code will be housed in a separate location. The data will be maintained under password protection in the database.

8.0 CODING OF DATA

The data set for recruitment (name, telephone number and Study ID number) and the data listed in Section 7.1 for analysis will be stored on a password secured database with access only to designated study team members and the PI.

9.0 STATISTICAL CONSIDERATIONS.

9.1 Sample Size Estimation and Justification

We anticipate needing to screen approximately 200 individuals to enroll up to 80 individuals and achieve a final sample size of approximately 47 evaluable participants. For our primary outcome (i.e. change in average sleep quality VAS scores), we assume a common standard deviation = 2 and a conservative 0.50 correlation between VAS scores. We will have at least 90% power to detect a mean VAS score difference of 1 with $\alpha = 0.05$ using a two-sided Wilcoxon signed-rank test for the difference between dependent means with a final sample of 47 participants. Previous research on participants with insomnia and depression have suggested that single item sleep quality score can effectively detect meaningful changes in sleep quality over time relative to lengthier questionnaires.¹⁶

The secondary objectives include evaluating changes in the ISI, GAD-7 and daytime alertness VAS score. As above, we anticipate at least 90% power to detect a 4.5-point change in the ISI and GAD-7 with an expected standard deviation of 5. For daytime alertness, we anticipate at least 90% power to detect a 1-point change with an expected standard deviation of 2.

9.2 Projected Study Timeline - Accrual, Data/Sample Collection, Completion

The final sample size for this observational study will be 47 participants.

We anticipate screening, enrollment and data collection to be complete in 3-4 months. Study closeout will be complete in 2 weeks, Data analysis will be complete in 2 months and a CSR and lay summary will be complete in 3-4 weeks. Altogether, the study duration is estimated to be 8 months.

The final analysis will take place after approximately 47 evaluable patients have completed all final study instruments. These activities will be completed approximately 29 days after enrollees initiate participation in the study.

9.3 Evaluable Participants

Participants will be considered evaluable for analysis if:

1. They complete all the study assessments, with at least 60% completed daily assessments in each arm (Product Use vs. No Product Use); AND
2. Objective sleep data from personal wearable devices are collected.

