9.6 Statistical Analysis Plan

The primary objective of this study is to determine the impact of Sip2Sleep® use on symptoms of sleep disturbance, as measured by the change in sleep quality VAS scores from 47 participants. Univariate statistics will be generated to describe the distribution of patient characteristics and outcome data. Continuous variables will be described using means, standard deviations, minimums and maximums while categorical variables will be described using counts and percentages. Sleep quality VAS scores will be compared from baseline pre-treatment; and at end of study (post-treatment) of the same individuals. We will enroll up to 80 participants to achieve at least 90% power to detect a mean change in sleep quality VAS scores of 1 points (SD=2) from baseline with a type I error of 0.05 (two-sided) assuming a paired means, dependent Wilcoxon Signed-Rank test. We are testing the null hypothesis that there is no difference between pre-treatment and post-treatment mean sleep quality VAS scores within study participants. Summary statistics will be generated, and paired differences between pre-treatment and post-treatment sleep quality VAS scores will be reported, along with 95% confidence intervals.

Additionally, parametric linear mixed models will be employed to simultaneously account for correlated observations and adjust for confounding variables (Proc Mixed, SAS). Several covariance structures, including compound symmetry and unstructured, will be evaluated by comparing AIC and BIC to identify optimal model fit. Random slope and intercept will also be considered in a similar manner. Patient characteristics (i.e. age and sex) will be included in adjusted models a priori for confounding control. Directed acyclic graphs will be employed to select other potential confounding variables and identify biases during the model fitting process. Large differences will be further examined and may help identify where further calibration of estimation models are needed.

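### The primary sleep-quality result rests on one completer set fixed after enrolment, with no wider outcome set or sensitivity analysis, and the 60% floor may not protect the weeks compared

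*Combined protocol and SAP*

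**What the plan says.** Section 9.3 defines the only set described as evaluable for analysis. Its first condition is "They complete all the study assessments, with at least 60% completed daily assessments in each arm (Product Use vs. No Product Use); AND". Its second is "Objective sleep data from personal wearable devices are collected".

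Three other sections rely on that set:

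- Section 9.1 plans to "enroll up to 80 individuals and achieve a final sample size of approximately 47 evaluable participants".
- Section 9.2 sets the trigger: "The final analysis will take place after approximately 47 evaluable patients have completed all final study instruments".
- Section 9.6 states the primary objective "as measured by the change in sleep quality VAS scores from 47 participants" and gives the contrast: "Sleep quality VAS scores will be compared from baseline pre-treatment; and at end of study (post-treatment) of the same individuals".

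Section 1.0 words the primary endpoint with two references, baseline and the week off product. It lists wearable measures under exploratory objectives only, for example "To observe the change in sleep duration via personal health tracking wearable device".

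Section 9.4 analyses demographic and baseline values on everyone, but says nothing comparable for outcomes. Section 9.5 will look at missingness in outcome variables, will consider multiple imputation when 5% to 40% of cases are missing, and restricts regressions to complete cases. Section 9.6 adds that "parametric linear mixed models will be employed to simultaneously account for correlated observations", without naming a wider set for those models.

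**The concern.** Membership of the analysis set depends on what participants do after they enrol. With no control group, the mean change among those who finish everything may differ from the mean change among all who entered the product periods. Nothing in the plan would show whether it does.

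The conditions also do not match the endpoint. The primary outcome is a daily self-rated score. The questionnaire and wearable conditions can remove someone whose daily scores are adequate. The one condition that does protect the VAS averages, the 60% floor, is set by arm (Product Use and No Product Use), while Section 9.6 compares baseline with end of study.

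Section 9.5 adds doubt about who is analysed. Planning for outcome variables missing in up to 40% of cases fits a looser reading of Section 9.3, and the complete-case rule for regressions fits a stricter one. Two analysts could build different sets from the same text.

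**Working it through.** **1. The plan's own figure.** Section 9.1 gives SD 2, correlation 0.50, difference 1, two-sided 0.05 and 90% power. SD of the paired difference = √(4 + 4 − 2 × 0.50 × 4) = 2, so the standardised effect is 1/2 = 0.5. The noncentral t needs 44. Dividing by the Wilcoxon efficiency 3/π = 0.955 gives 46.08, so 47. Power at 47 is 0.906 by this approximation and 0.908 by simulation with normal differences. The sample size reproduces and is not in dispute.

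**2. People outside the set.** At the enrolment ceiling: (80 − 47)/80 = 33/80 = 41%. If only 60 were enrolled (an assumed figure): 13/60 = 22%. Some of these may leave before product use starts on Day 8.

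**3. Questionnaires that can exclude.** The calendar in Section 4.0 and Section 6.1 schedule the ISI on Days 1, 8, 15, 22 and 29 (5), the GAD-7 on the same days (5) and one Experience Survey: 5 + 5 + 1 = 11 after enrolment. Section 9.3 relaxes completeness only for daily surveys.

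**4. The 60% floor under different readings.** Section 6.1 lists Baseline (Days 1–7), Product Use (Days 8–14), No Product Use (Days 15–21) and Product Use (Days 22–28).

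| Reading of the arm | Days | 60% | Surveys needed | Lowest count in a compared week |
|---|---|---|---|---|
| No Product Use = Days 15–21 only | 7 | 4.2 | 5 | Off-product week 5 of 7; baseline not covered |
| No Product Use = baseline plus Days 15–21 | 14 | 8.4 | 9 | Baseline 9 − 7 = 2 of 7 |
| Product Use = both product weeks pooled | 14 | 8.4 | 9 | Last product week 9 − 7 = 2 of 7 |
| Each product week separately | 7 | 4.2 | 5 | Last product week 5 of 7 |

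**5. Complete cases at daily level.** Under the pooled floor an evaluable person may miss 14 − 9 = 5 product-use days. If a complete case means no missing daily score, the mixed models lose that person. The Wilcoxon test is unaffected.

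**6. Which night a survey reports.** Footnote d in Section 4.0 says daily surveys ask about the night before. The Day 8 survey therefore reports a baseline night, and the Day 29 survey the last product night. By the same logic the Day 15 and Day 22 surveys belong to the period just ended. Each period then has seven surveys: Days 2–8, 9–15, 16–22 and 23–29.

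**7. Precision.** The 95% half-width is t(0.975, n − 1) × 2/√n: 0.59 at n = 47, 0.56 at 52, 0.53 at 57 and 0.49 at 67.

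**8. Illustration only.** Suppose the 47 improve by 1.0 and 10 further people with product-period data change by x. The mean is (47 × 1.0 + 10x)/57, which gives 1.00, 0.91 or 0.82 for x = 1.0, 0.5 or 0. The values of x are assumed; the documents give none.

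**The case against.** A prespecified evaluable set is defensible in an observational, consumer-driven study meant to inform later designs, provided it is labelled as such. Section 9.5 already plans to examine missingness and consider multiple imputation. This has some force, but imputation is only to be considered, variable by variable. It is assigned neither to the primary test nor to people outside the evaluable set. The mixed models could use partial data, but Section 9.5 restricts them.

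Other objections limit the point, and they stand:

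- **Attrition.** A reader might infer that the plan expects to lose 41%. It does not: 80 is an upper limit and the analysis is triggered by about 47 evaluable people.
- **The floor.** A reader might infer that the floor is unconnected to the comparison. It does cover the off-product week, which Section 1.0 names as a reference. The gap for baseline or the last product week depends on how arm and end of study are read. Section 4.0 gives End of Study its own column at Day 29.
- **The wearable condition.** Probably few people are lost. Section 3.2 requires a device, no minimum amount of data is set, and the same daily survey covers the wearable review and the sleep rating.
- **Complete cases.** The term may mean complete records, in which case no participant need be lost from the mixed models for missing days.
- **Who started product.** No product-intake record is listed in Sections 4.0, 6.1 or 7.1, so a wider set cannot be defined by actual intake without new data.

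**Conclusion.** The point holds. One completer set, defined by behaviour after enrolment, carries the primary result. Nothing in Sections 9.4 to 9.6 supplies a wider outcome set or a sensitivity analysis. Taken literally, the rule drops people with adequate VAS data for questionnaire or wearable data that the primary endpoint does not use.

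Its size is bounded only loosely. Up to 33 of 80 fall outside the set at the enrolment ceiling, and the gain in precision from keeping more people is modest. A reader might infer that the completer set inflates the effect. The documents give no dropout rates or reasons, so neither the direction nor the size of any bias follows from them.

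The floor and complete-case points are conditional on wording that the plan leaves open. They call for clarification and do not show that the test is invalid. The change should be made before analysis.

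**What to change.** 1. **Section 9.3: define evaluability by endpoint.** For the VAS endpoints require only daily VAS data. For the ISI and GAD-7 require only that instrument at the time points compared. Keep the wearable condition for the wearable endpoints alone. State that the 47 in Sections 9.1 and 9.2 counts people evaluable for the VAS.
2. **Sections 1.0, 9.3 and 9.6: name the periods compared** and reconcile the two descriptions of the contrast. Apply the existing 60% floor to each of those periods, baseline included (5 of 7). Assign each survey to the night it reports, so that Day 8 counts towards baseline and Day 29 towards the last product week.
3. **Sections 9.5 and 9.6: add a sensitivity analysis.** Fit the planned mixed model to all observed daily VAS scores from enrolled participants with at least one survey reporting a product-period night (Day 9 survey or later). This definition needs no intake record. For outcome data, replace the complete-case restriction with all available observations.
4. **Reporting.** Show the result in the current Section 9.3 set alongside, with the number excluded by each criterion.

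A missing-not-at-random shift is optional and would need a stated size.

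The cost is SAP wording and a little more programming, with no new data collection. The per-period floor may exclude a few people whom a pooled floor would admit, and the estimate may be less favourable.
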